General study design: MHD subjects aged 65-80 years with impaired exercise capacity and function will be randomized into two groups (30/group). One group will undergo a home-based exercise program and the other usual care over a 12 week period. This subject number allows for a drop-out rate of 20%, while maintaining 80% power to detect a significant difference in our primary end-point, peak VO_2 . After enrollment, all subjects will be encouraged to consume at least 1.2 g/kg/protein/day throughout the study. The 12-week program will include a 2-week clinic-based exercise instruction period with testing at baseline before intervention and after 6 and 12 weeks. Measures at baseline and 12 weeks will include body composition by anthropometrics and dual energy X-ray absorptiometry (DEXA), thigh muscle volume and composition by CT scan, muscle strength and function, cardiopulmonary exercise testing, QOL, cognitive function and nutritional, inflammatory, lipid and biochemical status. Muscle biopsies will be obtained at baseline and at 12 weeks and will be assayed for signaling proteins, and gene and protein expression of key muscle mass regulators. More limited interim testing will be performed at 6 weeks. In addition, two to three days after the 12-week study, a pilot sub-study will be performed to test whether a high-calorie leucine-rich protein supplement enhances exercise-stimulated anabolic signaling. At this time muscle biopsies will be taken. Overviews of the study measurements and timeline are presented in Appendices I and II.

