For recruitment we will draw on a large patient population within 30-40 miles of the VA Palo Alto Health Care System (VAPAHCS) with travel reimbursement provided. *For example, the nearby Satellite Healthcare Centers have agreed to actively support the identification and recruitment of subjects, with their Chief Medical Officer, [name], serving as a significant contributor to this study. They operate 30 stand-alone dialysis centers within a 40 mile radius the VA Hospital in Palo Alto. These centers treat a total of 5,000 dialysis patients, with approximately 25% of these patients on home dialysis. At any given time, approximately 2% of their total patient population is enrolled in a clinical trial. There are 6 Satellite Healthcare clinics within 10 miles of the VA Hospital in Palo Alto, which provide MHD services to roughly 1,000 patients; these clinics will be a primary source of patients for the study.* At Santa Clara Valley Medical Center, a Stanford affiliate, \approx 300 patients are treated with MHD and this facility has agreed to refer study subjects. Smaller dialysis clinics such as VAPAHCS ([name]), Stanford Medical Center ([name]) and community nephrologists (letters attached) will also serve as resources. Combined, these resources provide a pool of \approx 2,000 subjects in close proximity to our center. From prior experience, \approx 5% of subjects will meet inclusion criteria and agree to participate. This will provide an adequate enrollment pool. While we expect the recruitment of subjects to reflect the distribution of women and minorities in our area, a concerted effort will be made to recruit and include them in the study.

Study population and inclusion/exclusion criteria: Males and females aged 65-80 years undergoing MHD for at least three months and without other active/uncontrolled disease will be studied. Exercise and usual care groups will be *matched by age, body mass index (BMI), MHD duration, and protein intake* using a stratified randomization approach.

Inclusion criteria. MHD subjects with impaired exercise capacity and function will be considered for the study. Subjects will be required to be in the peak VO_2 range of 10 to 20 ml/kg/min, equivalent to moderate functional impairment in patients with heart failure (88; 89). Subjects will be required to have dialysis treatment for >3 months with an average $Kt/V \geq 1.2$, and be able to perform exercise safely. Racial

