Group Assignment. After screening and baseline testing, an independent third party investigator ([name], letter attached) will *match MHD subjects on age, body mass index (BMI), MHD duration, and protein intake*, and assign them randomly to the exercise or usual care study groups. At the end of 12 weeks of study this investigator will assign half of the subjects in each group to receive a blinded nutritional supplement (high calorie whey or placebo). The blind will be broken on completion of the study.

Dietary Control. Prior to entry into the study the subjects will be encouraged to consume 1.2 g protein/kg/day, per Kidney Disease Outcomes Quality Initiative (KDOQI) recommendations (92) and advised to maintain a steady intake. However, we realize that the recommended intake may not be achieved in some subjects. In order to adjust for variation in protein intake we will measure the subject's protein intake on 3 occasions during the month prior to entry into the study. Then when assigning subjects to the study groups, measured protein intake will be taken into account by the third part study assigner, so that the protein intake in the 2 study groups will be similar. Protein intake will be monitored by three-day dietary records and the normalized protein equivalent of nitrogen appearance (nPNA), a reflection of protein intake in stable conditions. nPNA is calculated from the urea generation rate by means of kinetic modeling using measurements of pre- and post-dialysis urea levels plus any urea lost in the urine in patients with residual renal function. After entry into the study nPNA is calculated weekly for the first two study weeks, then monthly. During the study period, there will be regular bi-weekly follow up counseling by a dietitian in an effort to ensure that both groups meet target dietary protein intakes

Safety Measures. Before screening, subjects will be informed of the nature of the study and the procedures to be performed, and will sign an approved consent form. Measures to monitor and ensure safety include a screening ECG, maximal exercise test, and medical approval (see screening). The cardiovascular exercise lab has extensive experience in conducting clinical studies and has a staff of experienced personnel. We do not expect any long-term side effects from the proposed interventions. The exercise program is well balanced and varied with aspects of strength and aerobic training. Subjects will

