Since this is a pilot sub-study carried out with a limited number of subjects after completion of the main 12 week study, we have adopted a unilateral exercise protocol in which the resting contralateral limb serves as a control. This protocol will allow us to gain considerable insight into the salutary molecular processes activated by exercise in ESRD subjects and to test whether these processes can be enhanced by provision of a leucine-rich supplement. In brief, two to three days after completing the primary 12-week study, subjects from both the exercise and usual care groups will be studied in which one limb is exercised for 15 minutes, after which the vastus lateralis muscles of both the exercised and the contralateral resting limb will be biopsied. *Half the subjects in each of these 2 main groups (12 subjects from each group) will be matched by BMI and age and randomized to either a placebo mixture or a high calorie nutrient supplement.* The nutrient supplement will consist of a high-calorie leucine-rich protein (whey protein) given at the start and end of the exercise session. The study consists of the following 4 groups, each undergoing acute, unilateral exercise:

- Group 1.** Regular exercise group plus placebo
- Group 2.** Regular exercise group plus nutrient supplement
- Group 3.** Usual care group plus placebo
- Group 4.** Usual care group plus nutrient supplement

An outline of the experimental protocol is illustrated in Figure 2, and a detailed protocol follows.

[figure not shown]
Figure 2. Acute Exercise, Muscle Biopsy, and Nutrient Supplement Protocol for Specific Aim 2

Biopsies will be obtained from the dominant limb after acute exercise and from the non-dominant limb following rest. A *single* biopsy of each limb will be taken from each subject. Tissue taken from the biopsies will undergo molecular analysis to answer the following questions:

[figure not shown]

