Primary endpoint, Specific Aim 1. For this analysis we have used data from a recent 12-week study by Storer et al (36) on the effects of endurance exercise versus no exercise (usual care) on cardiorespiratory and skeletal muscle function in MHD patients. Change from baseline for peak VO₂ was 22% (an increase) in the exercise group and 6% (a decrease) in the usual care group. These findings are consistent with an average increase from baseline of 17% in MHD patients participating in exercise-based rehabilitation programs reported in the literature (14). Similarly, our primary outcome will be comparison of the change in peak VO₂ for patients randomized to exercise vs. usual care. To calculate the desired sample size we used a two group t-test of equal means and calculated the per group sample size (East 5, Cytel Inc, copyright 2007). Given the desired values for the standardized effect size (the absolute value of the difference in group mean changes divided by the common standard deviation) and overall level of significance and power of the test, the required sample was calculated. To detect a difference in group mean changes of 17% in peak VO₂ for exercise vs. usual care, given a common standard deviation of 20% (based on Storer et al (36), using a standardized effect size of 0.85), 23 subjects/group would be required to complete the study to achieve statistical power of 80% with a two-sided test of significance at the 0.05 level. Appendix VII shows how the required sample size varies by the standardized effect size for power of 0.80 (solid curve) and 0.85 (dashed curve). Appendix VIII provides curves showing how the power varies by the standardized effect size for a per group sample size of 23 (solid curve) and 26 (dashed curve). For example, a per group sample of 23 provides power of about 0.17 and 0.38 to detect a small (0.3) and medium (0.5) standardized effect size, respectively. To allow for a 20% dropout rate we plan to enroll 30 subjects per group, or a total of 60. The 20% dropout rate is based on the PI's experience (87), and other similar research studies.

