Statistical analysis plan. Comparisons of clinical and demographic data between groups at baseline will be performed by the appropriate statistical test (for continuous variables, t-test for normally distributed data and Wilcoxon test for non-normal data; for categorical variables, chi-square test or Fisher's exact test). These comparisons will be performed at baseline only to assess adequacy of randomization. Comparisons between groups for cardiopulmonary exercise test, muscle biopsy, energy expenditure, cognitive function, and other functional measures before and after the study period will be performed by multivariate ANOVA; post-hoc comparisons will be made using the Bonferroni method. To analyze continuous variables measured at three or more time points we will use linear mixed effects regression (114). To explore the relationships between a given outcome and other variables, we will use multiple regression techniques. Since the reliability of a fitted regression model may be reduced if too many predictors are used (114), we will limit the number of predictors to four variables in each model ($\leq 1/10$ of the total). For the primary outcome, change in peak VO_2 , the specific independent variables in the model will include exercise compliance (average energy expended in kcals/week), change in muscle strength, and change in muscle mass. Missing data will be managed using the multiple imputation method which is preferable to older methods and described in detail by Schafer & Olsen (1999).

For Specific Aim 2 (effect of acute and chronic exercise on muscle wasting), we will employ a linear model, using period (baseline vs. 4 months) and treatment (exercise training vs. usual care) as independent variables along with their interaction (Bonferroni method). The intention to treat principal will be applied for all analyses.

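### Allocation is restricted on age, BMI, dialysis duration and protein intake, but the planned between-arm analyses do not include these factors, so some precision may be lost

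*Combined protocol and SAP*

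**What the plan says.** **Allocation.** Under Study population and inclusion/exclusion criteria, the two arms are to be "matched by age, body mass index (BMI), MHD duration, and protein intake" "using a stratified randomization approach". Group Assignment repeats the four factors. Dietary Control adds that protein intake, measured three times in the month before entry, is taken into account at assignment "so that the protein intake in the 2 study groups will be similar". No cut-points, number of strata or block size are given. In the sub-study (Approach to Specific Aim 2), subjects "will be matched by BMI and age and randomized to either a placebo mixture or a high calorie nutrient supplement".

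**Sample size.** For the primary endpoint, "we used a two group t-test of equal means and calculated the per group sample size". The calculation has no covariate term.

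**Analysis.** The Statistical analysis plan contains:
- baseline tests on clinical and demographic data, of which it says "These comparisons will be performed at baseline only to assess adequacy of randomization";
- multivariate ANOVA with Bonferroni post-hoc tests for before-and-after comparisons between groups;
- linear mixed models for variables measured at three or more times, with no covariates listed;
- exploratory multiple regressions limited to four predictors. The one for change in peak VO2 names energy expenditure, change in strength and change in muscle mass;
- for Aim 2, a linear model with period, treatment and their interaction.

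None of these names age, BMI, dialysis duration or protein intake, or a stratum, as a model term.

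**The concern.** Balancing a prognostic factor across arms removes that factor's contribution from the chance variation in the arm difference. An analysis that leaves the factor out still counts its variance as residual error. The test then assumes more noise in the treatment comparison than the design allows. Standard errors are too large, confidence intervals cover more often than their nominal level, and the true type I error falls below 0.05.

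What is at stake is precision. The protocol goes to some trouble to balance the arms, especially on protein intake, and an unadjusted analysis gives up part of the benefit. This matters in a small trial that reports power of only about 0.38 at a standardized effect of 0.5 with 23 per group.

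**Working it through.** **Inputs from the sample size section:** difference in mean change 17%, SD 20%, two-sided alpha 0.05, power 80%, 23 completers per group, 20% dropout, 30 enrolled per group.

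**Assumptions, not in the documents:** R², the share of outcome variance explained by the four factors together, taken as 0 to 0.3; and two levels per factor, giving 2⁴ = 16 strata of on average 60/16 = 3.75 subjects.

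**Step 1: the plan's own figures.** The standardized effect is 17/20 = 0.85. The exact noncentral t gives power 0.786 at 22 per group and 0.805 at 23, so 23 is right. At 23 per group, power is 0.169 for effect 0.3 and 0.382 for effect 0.5, matching the stated 0.17 and 0.38. For dropout, 23/0.8 = 28.75, rounded up to 29, which 30 per group covers. These figures all reproduce, and this point does not disturb them.

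**Step 2: limit under near-perfect balance.** The unadjusted standard error is too large by a factor 1/√(1−R²). True alpha is 2[1 − Φ(1.96/√(1−R²))].
- R² = 0.1: factor 1/√0.9 = 1.054; alpha 0.039
- R² = 0.2: factor 1/√0.8 = 1.118; alpha 0.028
- R² = 0.3: factor 1/√0.7 = 1.195; alpha 0.019

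**Step 3: a design closer to this one.** Sixteen small strata balance the factors only approximately, and dropout loosens the balance further. A simulation randomized 60 subjects in 16 median-split strata, with loss to 46 completers (2 × 23). It compared the two-group t-test (46 − 2 = 44 degrees of freedom) with analysis of covariance on the four continuous factors (46 − 6 = 40).

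| Assumed R² | True alpha, unadjusted | Limit from step 2 | Power at 0.85, unadjusted | Power at 0.85, adjusted |
|---|---|---|---|---|
| 0 | 0.050 | 0.050 | 0.80 | 0.78 |
| 0.1 | 0.044 | 0.039 | 0.79 | 0.81 |
| 0.2 | 0.042 | 0.028 | 0.81 | 0.87 |
| 0.3 | 0.036 | 0.019 | 0.82 | 0.91 |

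A second simulation, stratifying the 46 completers directly, gave adjusted power of 0.78, 0.83, 0.86 and 0.90 and adjusted alpha between 0.047 and 0.054. Differences of 0.01 to 0.02 in power between runs are therefore noise, and adjustment keeps alpha near its nominal level.

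**The case against.** The strongest reply is that R² may be close to zero. The primary outcome is change in peak VO2, and the Aim 2A response is the exercised limb minus the resting limb of the same subject. Age and BMI may predict the level of lean mass or thigh area, but stable differences between subjects largely cancel in such changes. In that case the unadjusted test is correct and four covariates cost about 2 points of power (0.80 to 0.78). This stands: the gain is conditional, and R² = 0 belongs in the range.

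The design is also unlikely to achieve near-perfect balance, so the step 2 alphas are limits and the step 3 values are the more realistic guide. This stands too.

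Several stronger readings are tempting but unsupported:
- *Published intervals are wrong.* The documents state no standard error or confidence interval for a planned result. The point concerns what the planned tests would produce.
- *Adjustment is ruled out, or the factors are used only in baseline tests.* The mixed-model covariates are unspecified and the peak VO2 regression names three predictors under a cap of four. The baseline tests cover clinical and demographic data without naming the four factors. Adjustment is not prespecified, which is a weaker statement.
- *Baseline tests will lead to a false claim of failed randomization.* The plan attaches no action to those tests and does not say how many variables are tested, so no error rate can be derived from it.

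**Conclusion.** The allocation and the analysis do not match: factors used to restrict randomization are absent from the stated between-arm models. When the factors are prognostic, the result is conservative inference. With 16 assumed strata and 46 completers, true alpha is about 0.036 to 0.044 for assumed R² of 0.3 to 0.1, with 0.019 to 0.039 as the near-perfect-balance limits.

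A reader might infer that the trial is underpowered or that its false-positive rate is inflated. Neither follows. Unadjusted power at the design effect stays at about 0.79 to 0.82, the treatment estimate is unbiased, and alpha is at or below 0.05. What may be lost is a gain of up to about 9 points of power at R² = 0.3 (0.91 − 0.82), or the corresponding narrowing of intervals. The sizes rest on assumed R² and assumed strata; the mismatch itself follows from the text.

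**What to change.** In the Statistical analysis plan:
- Prespecify age, BMI, dialysis duration and protein intake as continuous covariates in the between-arm comparison of change in peak VO2 and in the other full-sample between-arm comparisons. Continuous terms are preferable to stratum indicators, which would be too many for strata of about four subjects.
- Include BMI and age in the supplement comparison.
- State that the four-predictor cap applies only to the exploratory regressions, because treatment plus four factors is already five terms.
- Do not carry all four covariates automatically into the biopsy comparisons with 12 per group. There they would reduce the residual degrees of freedom from 24 − 2 = 22 to 24 − 6 = 18. State the choice for these analyses explicitly.

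For the full-sample comparisons the cost is a wording change and four model degrees of freedom, or about 2 points of power if the factors turn out not to be prognostic. No extra subjects or measurements are needed, since the factors are collected before assignment.

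Replacing the baseline p-values with a descriptive table is an optional reporting change and does not affect this point.

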A. Specific Aim 1 is designed to develop an effective, safe, low-cost aerobic and resistance exercise regimen. Because of the focus on improving cardiopulmonary function as well as muscle function and mass, both resistance and aerobic exercise will be components of the rehabilitation program. The program is modeled on a successful combined in-home/in-center study program administered by [name] at the VAPAHCS rehabilitation center for patients with cardiovascular disease with a mean age of 72 years (87). In general, exercise rehabilitation is highly effective in patients with cardiovascular disease (76), including the elderly (77; 78), and is associated with improved survival rates (76; 77; 79). Subjects randomized to the exercise group will undergo 12 weeks of exercise, including a 2-week ramp-up period conducted at the VAPAHCS rehabilitation facility. Subjects will be required to attend the facility twice a week on non-dialysis days during the initial 2 weeks of the study. These sessions will consist of 45-60 min of supervised exercise that combines aerobic and resistance training, including warm-up and cool-down. Throughout the study, subjects will be asked to perform 45 minutes of unsupervised aerobic exercise of their choice (such as walking) on non-dialysis days. Following the initial 2-week supervised period, subjects will be instructed to exercise on their own, and surveillance methods will be employed as previously described (87; 93) and outlined below. Following the 12-week study period, all subjects will undergo muscle biopsies. The following end-points will be measured at baseline and after the 12 week study period:

Primary Endpoint. Peak VO₂ is the primary outcome measure and is the gold standard for cardiopulmonary fitness. It incorporates elements of cardiac, pulmonary and muscle function known to improve with exercise.

Secondary Endpoints. These include lower and upper body strength, body composition, thigh muscle mass, muscle biopsy for protein signaling, quantitative muscle morphology and gene expression, daily activities, QOL, laboratory measures of cardiovascular risk factors, nutritional and inflammatory parameters as detailed below.

Together, these measures should allow us to determine whether the home-based exercise regimen is effective in counteracting loss of muscle function and mass common in elderly MHD patients, along with reducing cardiovascular risk.

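### The analysis plan does not carry over the peak VO2 t-test that the trial is powered on; it places the exercise test under multivariate ANOVA with Bonferroni post-hoc comparisons and an undefined family

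*Combined protocol and SAP*

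**What the plan says.** The Primary Endpoint paragraph under Specific Aim 1 names one endpoint: peak VO2 "is the primary outcome measure and is the gold standard for cardiopulmonary fitness". The power section (Statistics, Primary endpoint, Specific Aim 1) defines the contrast: "our primary outcome will be comparison of the change in peak" VO2 between the exercise and usual-care arms. It also states how the trial was sized: "To calculate the desired sample size we used a two group t-test of equal means", with 23 completers per group "to achieve statistical power of 80% with a two-sided test of significance at the 0.05 level". On enrolment it says: "To allow for a 20% dropout rate we plan to enroll 30 subjects per group, or a total of 60".

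The Statistical analysis plan then describes the methods:

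- A t-test (or Wilcoxon test) appears only for clinical and demographic data at baseline.
- Between-arm outcome comparisons are covered by one sentence. It opens "Comparisons between groups for cardiopulmonary exercise test, muscle biopsy, energy expenditure, cognitive function, and other functional measures" and continues "functional measures before and after the study period will be performed by multivariate ANOVA; post-hoc comparisons will be made using the Bonferroni method".
- Linear mixed models are reserved for variables measured at three or more time points.
- The one sentence that names the primary outcome describes a regression of change in peak VO2 on exercise compliance, change in strength and change in muscle mass. Treatment arm is not among the listed predictors.
- For Specific Aim 2, a linear model uses period and treatment "as independent variables along with their interaction (Bonferroni method").

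Item (2)(b) of the measurements section schedules the treadmill test at baseline and 12 weeks only.

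**The concern.** The power section and the analysis plan should describe the same primary test, and here they do not visibly do so. The exercise test has two time points, so the mixed model does not cover it. The t-test is confined to baseline, and the regression has no listed treatment term. That leaves the multivariate ANOVA sentence as the only method for the primary between-arm comparison. Taken literally, it puts peak VO2 in a joint test with other domains, followed by Bonferroni-adjusted comparisons, and it does not set the primary endpoint apart.

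Two things are at stake. The first is whether the stated 80% power belongs to the test that will be run. The second is whether the decision rule is fixed before the data are seen. A peak VO2 p-value of 0.03 is positive at 0.05 but negative at 0.05/2 = 0.025 or any smaller share. Two statisticians could each follow the text in good faith and reach opposite conclusions.

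**Working it through.** **Inputs from the power section.** Difference in mean change 17%, common SD 20%, so d = 17/20 = 0.85; two-sided alpha 0.05; target power 80%; 23 completers per group; 30 enrolled per group; 20% dropout, so 30 × 0.8 = 24 expected completers.

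**Method.** Exact two-sample t-test power. With n per group, df = 2n − 2 and noncentrality δ = d√(n/2). Power = P(|T| > t(1 − α/2, df)), where T is noncentral t with noncentrality δ.

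**Step 1: reproduce the plan's figure.** For n = 23, df = 44 and δ = 0.85 × √11.5 = 2.882. The critical value at 0.05 is 2.015 and power is 80.5%. For n = 22 it is 78.6%. So 23 is the smallest n that reaches 80%. Allowing for dropout, 23/0.8 = 28.75, or 29, and 30 is adequate. The sample size is correct for the test it assumes.

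**Step 2: the favourable reading.** With two arms and two time points, the group-by-time term for peak VO2 alone is the between-arm difference in mean change. Its F statistic is the square of the two-group t on change. Power stays at 80.5%.

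**Step 3: peak VO2 takes a Bonferroni share.** Replace α by 0.05/m. The plan gives no m, so the values below are assumptions for illustration.

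| m (assumed) | α | Power, n = 23 | Power, n = 24 | Power, n = 30 | Completers per group for 80% |
|---|---|---|---|---|---|
| 1 | 0.05 | 80.5% | 82.2% | 89.9% | 23 |
| 2 | 0.025 | 71.2% | 73.3% | 83.6% | 28 |
| 3 | 0.0167 | 65.3% | 67.7% | 79.3% | 31 |

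For m = 2 at n = 23 the critical value rises from 2.015 to 2.321 against the same δ of 2.882; for m = 3 it is 2.489. The n = 30 column is shown because the plan specifies intention to treat with multiple imputation. It is an upper bound, since imputed values do not carry the information of observed ones.

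**Step 4: a joint test.** Here power depends on effects on the other outcomes and on correlations, and the documents give neither. Two assumed cases for a two-outcome Hotelling T² at 0.05 with n = 23 show the spread. If only peak VO2 moves (d = 0.85) and the outcomes are uncorrelated, power is 70.3%. If both move by 0.85 SD with correlation 0.5, it is 82.8%. These are powers to reject the joint null, not to conclude on peak VO2. If the joint test were a gate before testing peak VO2 at 0.05, the two-step power could equal but never exceed that of the t-test alone.

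**The case against.** The strongest reply is that the power section already states the primary contrast and its alpha, directly before the analysis plan, and nothing later withdraws them. A prespecified primary contrast is not naturally called a post-hoc comparison. With one between-arm change contrast, Bonferroni would ordinarily apply to whatever follows it. The outcome sentence also reads more easily as a list of measures, each compared before and after, than as one joint vector. Biopsy comparisons are planned at 12 per group and have their own Aim 2 model, and energy expenditure is followed by weekly calls, which would place it under the mixed model. The Bonferroni note for Aim 2 belongs to a secondary aim with many molecular markers and says little about the primary endpoint.

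Most of this stands as an argument about likely intent. It rules out three stronger readings that a reader might infer. The documents do not show that Bonferroni will be applied to peak VO2. They do not show that the trial is underpowered or that 30 per group is too few. Nor do they support saying that 80% power is available only if peak VO2 is tested alone at 0.05: with all 30 per group analysed, a share of two comparisons still gives 84%, and some joint-test assumptions lose nothing.

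The reply does not remove the gap. A sample-size method is not an analysis specification. The section that is meant to specify the analysis gives a different method for the exercise test, without an exemption, a defined family or a count.

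**Conclusion.** The point holds as a mismatch between the powered test and the analysis plan, and it should be fixed. The plan's 23 per group is right for a single t-test on change in peak VO2 at two-sided 0.05 (80.5%), but the Statistical analysis plan does not commit to that test.

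The consequence depends on the reading. It is nil if a group-by-time test of peak VO2 alone is meant. If peak VO2 takes a share of 2 or 3 comparisons, power at 23 per group falls by about 9 or 15 percentage points. The loss is undetermined under a joint test. The Bonferroni figures rest on the plan's own d = 0.85 and on assumed numbers of comparisons. No design number is shown to be wrong. The open decision rule for the primary endpoint remains a weakness whichever reading was intended.

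**What to change.** Add to the Statistical analysis plan: *The primary analysis is the single between-group comparison of the 12-week change in peak VO2 (two-group t-test on change, equivalently the group-by-time term) at two-sided 0.05. It lies outside the multivariate ANOVA and outside any Bonferroni family.* Then confine the multivariate ANOVA and the Bonferroni adjustment to secondary endpoints.

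If the present wording is kept instead, state the number of comparisons in the family and restate the power at the alpha actually used for peak VO2.

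The cost is two or three sentences of SAP wording. No patients, visits or data are added, and the first option keeps the planned 60 subjects and the stated power.
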